#### **Data processing and statistical analyses**

##### *Accelerometry*

PA was assessed by waist-mounted accelerometry. The device was mounted with an elastic belt. In the four pre-policy studies ActiGraph monitors (AM7164, GT1M, and GT3X) were used. In the post-policy study, Axivity AX3 accelerometers were used. The Axivity AX3 instrument stores raw acceleration, whereas the main output of Actigraph monitors is counts per time unit. A newly developed aggregation method enables the generation of Actigraph counts from raw acceleration with very high agreement (6), which enables harmonization of PA data across different instruments. Data were processed using 10-seconds epochs.

Since timetables were not available in all pre-policy studies, aggregated acceleration data by age group and study were used to create PA intensity trajectories for each weekday represented. In these, a clear pattern appeared during the school hours due to the constant shift between class and recess. The trajectories made it possible to identify a group level *morning wake time, evening to bedtime and start and end of school day*. Subsequently, these time points were used to define: i) school time and ii) total time (from morning till bedtime). The time point identification was done by two researchers separately and then compared to ensure data quality. Moreover, the time points were compared to timetables available in the post-policy population.

PA levels will be examined from 2009-2018. During the same period, it is anticipated that the length of the school day has expanded due to the 2014 school policy, which will influence the total school time participants have available to accumulate PA. As a supplement, a standardized 8.10am-1pm school time variable was conducted, which controls the effect of school length. Both the standardized school time variable and the school time variable based on the above-mentioned trajectories will be used to examine the primary aim.

i) School- and ii) total PA will be examined using following PA outcomes:

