#### *Statistical analyses*

All analyses will be conducted in StataBE 17 (StataCorp).

All outcomes are continuous. Thus, a linear mixed-effect model approach will be used to examine any changes in PA levels over time. Time will be treated as a categorical variable in which each year (2009, 2010, 2012 and 2017/18) represents a category. A newly published Danish report based on objective data from the post-policy population reports differences in PA levels among boys and girls and different age-groups during school time (9), and analyses will therefore be adjusted for age and gender. Moreover, analyses will be adjusted for seasonal variations (10). Project, school-identifier and individual identifier will be modelled as random effects due to the assumption that observations within these clusters are not independent, and individual identifiers are nested in schools, which are nested in projects. We assume that the effect of the school policy might be different in the younger school children compared to the older ones. Thus, an interaction term or stratification will be utilized to account for this.

Initially, pre-policy trends ( $t$ : 2009, 2010 and 2012) will be inspected.  $t$  denotes time ( $t=2009, 2010, 2012, 2017/18$ ) and  $b(t)$  denotes reference-category contrasts describing the effect of time  $t$  with  $t=2009$  as reference category. Firstly, we will test pre-policy linearity in  $b(t)$  ( $H_0: b(2010)=b(2012)/3$ ). If linearity exists, we will test for a constant pre-policy level in  $b(t)$  ( $H_0: b(2010)=b(2012)=0$ ). If the pre-policy trend is either

linear (positive or negative) or constant, we will analyze post-policy data using mixed-effect linear regression testing either i) whether linearity (positive or negative) continues post-policy ( $H_0: b(2010) = b(2012)/3 = b(2017/18)/8.5$ ) or ii) no difference between pre- and post-policy, if the pre-policy trend is constant ( $H_0: b(2010)=b(2012)=b(2017/18)=0$ ). This will be examined using post-estimation testing of linear combinations of coefficients. If no linear trend exists in pre-policy data, a bootstrap method will be implemented testing whether  $b(2017/18)$  significantly exceed any pre-policy estimates in  $b(2009)$ ,  $b(2010)$  or  $b(2012)$ . If using the bootstrap method, we will make no assumptions regarding pre-policy trends in  $b(t)$ .

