#### **Codebook:**

Variable name	Variable Label	Variables types	Legal values	Value labels
id_project	Individual and project identifier	Categorical/nominal		
gender	Boy or girl	Categorical/dichotomous	0, 1	0: Girl, 1: Boy
age	Age at examination	Continuous	6-18	
school_level	School level at examination	Categorical/dichotomous	1, 2	1: 0th-5th grade, 2: 6 th -9th grade
grade	Academic school year	Categorical/ordinal	1-9	1: grade 1, 2: grade 2 etc.
school_at_examination	School at examination	Categorical/nominal	1-57	1: school 1, 2: school 2 etc.
year	The year of data collection	Categorical/nominal	2009, 2010, 2012, 2017/18	2009, 2010, 2012, 2017/18
season	The season of data collection	Categorical/dichotomous	1, 2	1: spring/summer, 2: fall/winter
project2	Project over time - FASER matched with historical projects	Categorical/nominal	1-4	1: CHAMPS, 2: EYHS, 3: NBBB, 4: SPACE
Intervention	Pre- or post-intervention	Categorical/dichotomous	0, 1	0: Pre-intervention, 1: Post-intervention
category	The day is divided in 4 categories (events)	Categorical/nominal	1- 5	1: school time (timetable), 2: school time (standard 8.10-13), 3: Leisure time, 4: Total (full day)
Duration	Duration of events in minutes (categories above)	Continuous		
Weekday	Day of the week	Categorical/nominal	1-5	1: mon, 2: tue, 3: wed, 4: thur 5: fri

DayNumber	Day of recording	Categorical/nominal	1-8	1: First measurement day, 2: Second... etc.
non-wear	Minutes of non-wear	Continuous		
Cpm	Average counts per minutes	Continuous		
mvpa_min	Minutes of moderat to vigorous physical activity (>2296 counts)	Continuous		
movement_min	Minutes of movement (>753 counts)	Continuous		

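### The mixed model has no school-by-year (or grade-within-school-by-year) random effect, so the standard errors of the year contrasts may be too small

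*SAP*

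**What the plan says.** Under Statistical analyses, the SAP specifies a linear mixed model with three random effects: "Project, school-identifier and individual identifier will be modelled as random effects due to the assumption that observations within these clusters are not independent". It states further that "individual identifiers are nested in schools, which are nested in projects". The fixed part holds year ("Time will be treated as a categorical variable in which each year (2009, 2010, 2012 and 2017/18) represents a category"), and the SAP adds that "analyses will therefore be adjusted for age and gender" and that "analyses will be adjusted for seasonal variations". An interaction or stratification for younger versus older pupils is also planned.

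The Background section says that the 31 post-policy schools were also part of the pre-policy studies. The codebook gives one school variable with codes 1 to 57, and a project variable in which post-policy data carry the code of the matched historical project. The school and project intercepts are thus shared across the periods being compared.

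The codebook also holds a grade variable ("Academic school year"), which has no role in the model. There is no class identifier.

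**The concern.** The SAP justifies its random effects by non-independence within clusters. The same reasoning applies to children measured together in one school in one year. They may share that year's staffing, lesson plan, weather or local events, and where school hours are set at group level they may also share any error in that time window. A school intercept that is constant over time cannot absorb a deviation that belongs to one wave only. Fixed terms for age, gender and a two-level season remove average differences, not those specific to one school and year.

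The model would then count children as more independent than they are. Three decisions use the resulting standard errors: the pre-policy linearity test, the constancy test and the post-policy test. A false rejection of linearity also sends the analysis to the bootstrap branch. The planned assumption checks cover normality, homoscedasticity and linearity, and none is aimed at this clustering.

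**Working it through.** The SAP states no sample size, intraclass correlation (ICC) or standard error, so there is no figure of its own to reproduce. The check asks how far the model standard error falls short if year-specific clustering is present.

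**Inputs from the SAP.** 31 post-policy schools, all also measured before the policy; school codes 1 to 57; random effects for project, school and individual; four year categories.

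**Assumed inputs.** Each school in one pre-policy year; 3 grades per school and wave; 20 (or 10) children per grade, school and year; SDs of 5 min (school), 12 min (child) and 18 min (day); 5 days per child; grade-by-year SD of 2, 3 or 4 min.

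**Step 1: variance of a child's mean within a cell.** 12² + 18²/5 = 144 + 64.8 = 208.8. With the school variance of 25 added, grade-by-year SDs of 2, 3 and 4 min make up 4/237.8 = 2%, 9/242.8 = 4% and 16/249.8 = 6% of the total.

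**Step 2: hand approximation for a within-school change.** The model gives a cell mean the variance 208.8/m; the true variance is σ² + 208.8/m, where σ is the grade-by-year SD. The ratio of model to true standard error is √[(208.8/m) / (σ² + 208.8/m)].

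| m | σ (min) | Ratio |
|---|---|---|
| 20 | 2 | √(10.44/14.44) = 0.85 |
| 20 | 3 | √(10.44/19.44) = 0.73 |
| 20 | 4 | √(10.44/26.44) = 0.63 |
| 10 | 2 | √(20.88/24.88) = 0.92 |

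**Step 3: full layout.** The values to which a REML fit with school intercept and child residual converges, compared with the true standard errors, give ratios of about 0.87, 0.76 and 0.67 at 20 per cell. Across the year contrasts the range is about 0.88 (SD 2) to 0.65 (SD 4). At 10 per cell and SD 2 the ratio is about 0.93. These lie slightly above the hand values because the fitted school and residual variances absorb a little of the omitted term.

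**Step 4: effect on a nominal 5% test.** By normal approximation, the rejection rate under no change is 2Φ(−1.96 × ratio): 6.8% at 0.93, 8.5% at 0.88 and 20% at 0.65. Simulation of similar layouts (cells of 15 or 20; two runs of 600 and 400 data sets per setting) agrees. At SDs of 2, 3 and 4 min, 2017/18 against the pre-policy mean rejected in about 9%, 12–15% and 16–22%. The linearity test rejected in 6–9%, 9–12% and 12–19%. With no grade-by-year effect the rates were 5–7%.

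**Step 5: a model that includes project, in ICC terms.** Assumed: school ICC 0.05, project ICC 0.01, 3 grades per school.

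| Omitted component | Ratio |
|---|---|
| Stable grade-within-school effect, ICC 0.01–0.10 | 1.00–1.04 |
| Grade-by-school-by-year, ICC 0.01, 10 per cell | 0.96–0.97 |
| Grade-by-school-by-year, ICC 0.05, 10 per cell | 0.84–0.86 |
| Grade-by-school-by-year, ICC 0.05, 25 per cell | 0.67–0.69 |
| Grade-by-school-by-year, ICC 0.10, 25 per cell | 0.54–0.55 |
| School-by-year, variance 0.01, 0.03, 0.05, 25 per cell | about 0.77, 0.56, 0.46 |

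**Step 6: which term repairs it.** Layout of step 3, balanced, 20 per cell, ratios for the single year effects:

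| Grade-by-year SD | School-by-year SD | Grade term only | School-by-year term |
|---|---|---|---|
| 3 | 0 | 1.00 | 1.00 |
| 3 | 2 | 0.84–0.86 | 1.00 |
| 3 | 3 | 0.74–0.77 | 1.00 |
| 0 | 3 | 0.64–0.66 | 1.00 |

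With 2017/18 against the pre-policy mean included, the grade term alone leaves 0.62–0.86 in the last three rows.

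**The case against.** A reader might infer that all year-effect standard errors are certainly too small because children in one grade of one school share a timetable and a measurement period. The SAP does not support that.

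- It nowhere says that a grade shares either. It says that timetables were missing in some pre-policy studies, and that calendar periods and age groups were matched to those studies.
- The Accelerometry section reports that "a clear pattern appeared during the school hours due to the constant shift between class and recess", but those trajectories were pooled by age group and study. A pattern that survives pooling across schools shows timing common to schools. It is not evidence that one grade of one school departs from the others.
- A stable grade-within-school effect largely cancels in the pre-post comparison (ratio 1.00–1.04). Only a year-specific component does harm, and with ICC 0.01 and 10 children per cell the loss is trivial.
- Lesson mix and teacher belong to the class as much as to the grade, so grade is at best a proxy. The mechanism is also weaker for overall PA, which includes leisure time.

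All of this stands, and it limits the point to a conditional one. There are also limits to the check. Steps 2 to 4 and 6 leave out the project effect. The simulated post-policy contrast is not the SAP's joint test, and the constancy test was not simulated. The bootstrap branch depends on its resampling unit rather than on model standard errors.

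What the objection does not remove is the structural gap: the model has no term that varies by school and year, although the same schools appear in both periods. If that variance is near zero, adding the term changes almost nothing.

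**Conclusion.** The point holds in conditional form. The planned model treats children measured in the same school and year as independent given a time-constant school intercept. If year-specific clustering exists at school or grade level, the standard errors of the year contrasts are too small and the tests based on them reject too often.

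The size is unknown. Under the assumed components, grade-by-year clustering gives ratios from 0.97 (negligible) to 0.54, and 0.88 to 0.65 in the 20-per-cell layout. School-by-year clustering costs more at equal variance. The SAP does not establish that the effect is present, nor that every year effect is affected. A grade term on its own would be an incomplete repair, since it leaves the standard errors too small wherever schools also vary by year.

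**What to change.** In Statistical analyses, add a random intercept for school-by-year (school_at_examination × year) between the school and individual levels. Where several grades per school were measured, nest grade within school-by-year inside it. Run the linearity, constancy and post-policy tests from that model, and report the estimated variance components.

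If only one grade per school was measured in a wave, the two terms coincide and school-by-year alone suffices.

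If the grade term is used, reconcile the codebook: the legal values of grade run from 1 to 9, while the lower category of school_level includes 0th grade, so those children would have no valid grade cluster.

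The cost is one or two extra random terms built from variables already in the codebook, and somewhat wider confidence intervals.

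### After linearity is accepted, constancy is tested with 2 df instead of a 1-df slope test, so linear drift is missed somewhat more often than the data require

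*SAP*

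**What the plan says.** The section Statistical analyses of the SAP sets up b(t) as "reference-category contrasts describing the effect of time" t, with 2009 as reference, and then fixes a sequence.

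- Step 1: "Firstly, we will test pre-policy linearity in" b(t), with null "H_0: b(2010)=b(2012)/3". This is one restriction.
- Step 2, reached only if step 1 does not reject: "If linearity exists, we will test for a constant pre-policy level in" b(t), with null "H_0: b(2010)=b(2012)=0". These are two restrictions.
- Final test if the pre-policy trend is judged linear: "H_0: b(2010) = b(2012)/3 = b(2017/18)/8.5".
- Final test if it is judged constant: "H_0: b(2010)=b(2012)=b(2017/18)=0". This null has no trend term.

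Of the final tests the SAP says: "This will be examined using post-estimation testing of linear combinations of coefficients". I take the two preliminary tests to be Wald tests of the same kind. No significance level is given for any step.

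**The concern.** Under the linearity accepted in step 1, the contrasts for 2010 and 2012 are slope × (1, 3), with a single free parameter. What remains to be asked is whether that slope is zero. Step 2 asks it with a joint test whose two restrictions include the one just accepted. The linearity part of the statistic has already been screened to be small, but it still raises the critical value.

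The direction matters. A cautious preliminary test is often harmless, but here non-rejection selects the final null with no trend. A drift missed over three pre-policy years is then carried to 8.5 years and appears as a pre/post difference in the primary analysis.

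**Working it through.** The SAP gives no level or power for these steps, so there is no plan figure to reproduce.

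**Inputs.** From the SAP: time points 0, 1, 3 and 8.5 years; the two preliminary nulls; their order. Assumed: alpha 5% for each test (range 1% to 10% below), and large-sample Wald tests.

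**Decomposition.** Let b = (b(2010), b(2012)) with covariance V, L = (1, −1/3) and x = (1, 3).

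- Step-1 statistic: W1 = (L′b)² / (L′VL), 1 df, cut-off 3.841.
- Slope statistic under linearity: G = (x′V⁻¹b)² / (x′V⁻¹x), 1 df, cut-off 3.841.
- Step-2 statistic: W2 = b′V⁻¹b, 2 df, cut-off 5.991.

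The covariance of L′b and x′V⁻¹b is L′x = 1 − 3/3 = 0. Hence W1 and G are independent and W2 = W1 + G for any V. Simulation with three sets of unequal year variances agreed to about 1e-14.

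After step 1 is passed, the slope part must exceed 5.991 − W1. That bar lies between 5.991 − 3.841 = 2.150 and 5.991. It is above 3.841 whenever W1 is below 2.150, which is the usual case if the trend is linear.

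**Level, given step 1 is passed and the level is truly constant.** P(step 1 passed) = 0.950 and P(step 1 passed and step 2 rejects) = 0.0251, so the conditional level is 0.0251 / 0.950 = 2.6%. At alpha 1% it is 0.6% and at 10% it is 5.1%, about half the nominal level each time. With F tests it is 2.2% at 5 denominator df and 2.6% at 50.

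**Power against exactly linear drift, given step 1 is passed.** With λ = slope/SE, integrate P(|Z + λ| > √(5.991 − u²)) over a standard normal u with |u| < 1.96, and divide by 0.95.

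| λ | 1-df slope test | SAP step 2 | Loss (points) |
|---|---|---|---|
| 1.00 | 17.0% | 10.6% | 6.4 |
| 1.96 | 50.0% | 37.7% | 12.3 |
| 2.48 | 70% | 58% | 12 |
| 2.80 | 80.0% | 69.5% | 10.5 |
| 3.24 | 90.0% | 82.7% | 7.3 |

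The largest loss is 12.6 points, at λ of about 2.2.

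**Consequence when the drift simply continues and the policy has no effect.** The probability of entering the constant branch is 0.95 × (1 − power):

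- λ = 1.96: 0.95 × 0.623 = 59.2% (SAP) against 0.95 × 0.500 = 47.5% (slope test), a gap of 11.7 points.
- λ = 2.80: 0.95 × 0.305 = 28.9% against 0.95 × 0.200 = 19.0%, a gap of 9.9 points.

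With assumed variances equal in the pre-policy years and half that in 2017/18, the final 3-df test rejects almost always in these cases. The false-claim rates are therefore the same figures: 59% against 48%, and 29% against 19%. With a 2017/18 variance four times the pre-policy one they are 48% against 37%, and 29% against 19%. For a smaller drift (λ = 1, half variance) they are 75% against 69%.

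**The case against.** **The joint null is what constancy means.** With time categorical, a constant level is exactly both contrasts being zero, and the test has its nominal level when run alone. This stands. A reader might infer that the test is invalid, or that the plan breaks a promised 5% level. The document supports neither reading: it states no alpha and promises no conditional level. The point is one of efficiency, given the order in which the tests are run.

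**Passing step 1 does not establish linearity, and the joint test keeps some sensitivity to other shapes.** This also stands, and it limits the gain. If the linearity contrast is truly off by 2 SE and still passes, power at λ = 2 is 48.4% for the SAP test against 51.6% for the slope test. For an isolated shift in 2010 the two are close at 2 SE (5.3% against 6.1%), and the order reverses slightly at 3 SE (8.1% against 7.5%). Still, screening out non-linearity is the job of step 1, and data failing it go to the bootstrap branch.

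**Most of the harm comes from pre-testing itself.** This is correct. About 48 of the 59 points and 19 of the 29 points of false claims remain with the slope test.

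**Conclusion.** The point holds as a moderate loss of efficiency with a cheap remedy. Run after step 1, the 2-df test is less able to detect linear drift than a slope test on the same data. The loss is at most about 12.6 points of power, and it narrows if the true trend is not exactly linear. Where the slope test has 50% to 80% power, continuing drift is read as a pre/post difference roughly 10 to 12 points more often; for smaller drifts the gap is less (6 points at λ = 1).

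The decomposition needs no assumption about the covariances. The percentages rest on alpha 5% for each test and on large samples. The false-claim rates rest also on assumed variances.

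A reader might infer that the slope test would cure the drift problem. It would not: at λ = 2, 48% of drifting data that pass step 1 would still be called constant. A constant verdict should not be read as proof of no drift under either test.

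**What to change.** Replace the step-2 null by a 1-df test of zero slope with b(2010) = b(2012)/3 imposed. In practice, refit the model with pre-policy time continuous at 0, 1 and 3 years plus an indicator for 2017/18, and test the time coefficient. State alpha for each preliminary test.

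The SAP dates the analyses to February and March 2022. If they are done, report the slope test as a sensitivity check on which branch was taken.

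The change costs one sentence and one refit. The downside is small: with no drift, the less precise linear branch is entered in 5% rather than 2.6% of cases that pass step 1. In one set of simulations this lowered power for a real policy effect by about 1 point (73.6% to 72.6%). Add a sentence that a constant verdict does not exclude drift.

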**Background**

In 2014, the Danish Government introduced a new school policy requiring an average of 45 minutes physical activity (PA) daily during the school day. The overall objective of this natural experiment is to examine the effectiveness of this national school policy on objectively-measured PA levels among Danish school-aged children aged 6 – 17 years between 2009 – 2018 (1). PA was measured by accelerometry during a 7-day period in children from 31 schools in 2017-2018 (post-policy) and compared to data from four historical school-based studies conducted between 2009-2012 (pre-policy) (2-5). All invited schools in the post-policy

population were represented in the pre-policy study populations, and calendar periods of data collection and age groups were matched according to the four historical studies.

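### The pre- versus post-policy test in the constant branch has 3 degrees of freedom, two of which only repeat the constancy pre-test

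*SAP*

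**What the plan says.** The SAP, Statistical analyses, codes time in four categories: "Time will be treated as a categorical variable in which each year (2009, 2010, 2012 and 2017/18) represents a category". With 2009 as reference there are three free coefficients, b(2010), b(2012) and b(2017/18). Two preliminary tests come first: linearity, b(2010)=b(2012)/3, and then constancy, b(2010)=b(2012)=0. They decide which policy test is used.

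- Constant branch: the test is described as "no difference between pre- and post-policy, if the pre-policy trend is constant", with the null "b(2010)=b(2012)=b(2017/18)=0".
- Linear branch: the test asks whether the line continues, with the null "b(2010) = b(2012)/3 = b(2017/18)/8.5".

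The section says that linear combinations of coefficients will be tested after estimation, but these joint nulls are the only ones it writes out for the two branches. It states no alpha. The Codebook lists an Intervention variable ("0: Pre-intervention, 1: Post-intervention") that the Statistical analyses section does not use.

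**The concern.** These are the tests of the primary aim whenever the pre-policy data look constant or linear. The constant-branch label promises one comparison, 2017/18 against the pre-policy level. The printed null is equality of all four periods, and two of its three restrictions involve no post-policy data and have just been tested.

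The linear-branch null does match its label, but one of its two restrictions repeats the linearity test.

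Two things are at stake. A rejection does not by itself show that 2017/18 departs from the pre-policy level or line, nor in which direction. A non-rejection may only reflect degrees of freedom spent on restrictions already examined.

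**Working it through.** The SAP gives no alpha, standard error or sample size, so it has no figure to reproduce. The figures below are large-sample Wald results. They assume 5% for every test unless stated, and preliminary and final tests taken from the same fitted model.

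**1. Degrees of freedom** (rank of the restrictions on b(2010), b(2012), b(2017/18))

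| Test | df |
|---|---|
| Linearity pre-test | 1 |
| Constancy pre-test | 2 |
| Constant-branch policy test | 3, of which 1 is new |
| Linear-branch policy test | 2, of which 1 is new |

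**2. Decomposition.** In one fit, the joint statistic equals the pre-test statistic plus a 1-df policy part:

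- constant branch: W3 = W2 + W1, where W1 compares 2017/18 with the common pre-policy level;
- linear branch: joint statistic = linearity statistic + a 1-df departure of 2017/18 from the line.

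**3. Evidence required of the policy part.** The 5% critical values for 1, 2 and 3 df are 3.841, 5.991 and 7.815.

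- Constant branch, pre-policy years agree exactly (W2 = 0): W1 must exceed 7.815, p = 0.005.
- Constant branch, pre-test just passed (W2 = 5.991): W1 must exceed 7.815 − 5.991 = 1.823 (unrounded values), p = 0.177.
- Linear branch: from 5.991 (p = 0.014) down to 5.991 − 3.841 = 2.150 (p = 0.143).

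**4. Type I error.** The pre-test part is capped at 5.99 < 7.815 (constant) or 3.84 < 5.991 (linear), so pre-policy differences alone cannot reject. With pre-tests at 1% the caps become 9.21 and 6.63. Both exceed the 5% final critical values, and pre-policy differences alone could then reject. The SAP does not exclude this.

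**5. Power without conditioning on the branch** (non-central chi-square)

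| Noncentrality | 1 df | 2 df | 3 df |
|---|---|---|---|
| 7.849 | 80% | 70.9% | 64.5% |
| 10.507 | 90% | 83.5% | 78.4% |
| 18.372 | 99% | 97.7% | 96.3% |

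**6. Size and power given entry to the constant branch.** This was simulated with both pre-tests applied in the SAP's order, independent year means, equal SEs and years coded 0, 1, 3, 8.5.

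- With no effect and no trend, the joint test rejects in 1.9% and the 1-df test in 5.0%.
- With the 80%-power effect, the figures are 62.1% and 80.0%. Most of that gap is size: run at 1.9%, the 1-df test has 67.6%, so the like-for-like loss is 67.6 − 62.1 = 5.5 points.
- Pre-tests at 10%: joint size 1.4%, power 60.4%. Pre-tests at 1%: 3.6% and 63.9%.

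**7. An undetected trend that merely continues, given entry to the constant branch.** The 1-df noncentrality for slope s (in SE of a year mean per year) is (7.167 s)²/1.333, since 8.5 − 4/3 = 7.167 and the contrast variance is 1 + 1/3 = 1.333.

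| Slope s | Branch entered | 1-df at 5% | Joint | 1-df at 1.9% |
|---|---|---|---|---|
| 0.1 | 92% | 9.5% | 4.0% | 4.4% |
| 0.2 | 91% | 23.7% | 12.3% | 13.5% |
| 0.3 | 89% | 46.1% | 29.3% | 31.4% |

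At 0.5 the 1-df test rejects in 87% and the joint test in 76% (77.5% against 75.8% at equal size).

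**8. Contrast against a continuing line.** The pre-policy years 0, 1, 3 have mean 4/3 and sum of squares 42/9 = 4.667. The variance is 1 + 1/3 + 7.167²/4.667 = 12.339, so the SE is √(12.339/1.333) = 3.04 times that of the constant contrast.

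**The case against.** The strongest reply is that the joint test is valid and conservative. With equal alpha and one fit, every rejection needs some post-policy contribution. The p = 0.177 limit is an extreme: given entry to the constant branch, about 13% of joint rejections under no effect and no drift have a policy contrast with p > 0.05, and 0.6% do under the 80%-power effect. Most of the conditional power gap is conservatism. A 1-df contrast also misreads an undetected continuing trend as a policy effect, and does so more often. The signed b(2017/18) comes from the same fit, and the wording on linear combinations leaves room for a 1-df contrast. Intervention equals 1 exactly when the year is 2017/18, so its absence from a model with categorical years is not an inconsistency.

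Much of this stands as qualification. The extreme p-value should not be taken as typical. The same-fit condition matters, because the SAP inspects pre-policy trends first and does not say from which fit; since b(t) is defined over all four periods, a single fit is the natural reading. The codebook point shows only that the variable needed for the fix already exists.

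The reply does not remove the concern. The decisive contrast is not printed, and b(2017/18) is a comparison with 2009 alone, not with the pooled pre-policy level. The joint test's apparent protection against trend nearly vanishes at equal size: 4.0, 12.3 and 29.3% against 4.4, 13.5 and 31.4%. That distortion comes from reading a non-significant pre-test as constancy, and both tests share it.

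**Conclusion.** The concern holds and should be fixed. The mismatch between label and null, and the overlap with the pre-tests, follow from the printed hypotheses and need no assumption.

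The consequence is lost power and unclear interpretation, not inflated type I error, provided all tests use 5% and come from one fit. Under a 5% assumption, 80% power falls to 64.5% in the constant branch and 70.9% in the linear branch. Given entry to the constant branch, the loss at equal size is about 5.5 points. The conditional figures also assume independent, equally precise year means. The actual loss in this study cannot be computed from the SAP.

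**What to change.** Keep the linearity and constancy tests as diagnostics, state their alpha, and state that they come from the same fit as the policy test. Prespecify one 1-df policy contrast per branch, with estimate and 95% CI:

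- **Constant branch:** the coefficient of Intervention in the same mixed model (same covariates and random effects), with the pre-policy years held at a common level.
- **Linear branch:** the coefficient of Intervention in the same model with a linear year term coded 0, 1, 3, 8.5.

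Do not replace these by a simple precision-weighted mean or line through the pre-policy estimates. Schools and projects are shared across periods: the Background says all invited post-policy schools "population were represented in the pre-policy study populations", the Codebook defines project as "Project over time - FASER matched with historical projects", and the model treats "individual identifiers are nested in schools, which are nested in projects". The 2017/18 estimate can therefore be correlated with earlier years. As an illustration, with unit variances and assumed correlations of 0.1, 0.5 and 0.3 with 2009, 2010 and 2012, generalised least squares weights those years 0.13, 0.53 and 0.33 (contrast variance 0.653). Equal thirds give 0.733.

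In the constant branch, also report the linear-trend contrast with its CI as a sensitivity analysis, not as a second test that must be passed. Given entry to that branch, it rejects a continuing trend of 0.1, 0.2 or 0.3 SE per year in only 3.0, 2.8 and 2.7%. Its power is just 14% for an effect with 80% power on the constant contrast.

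The cost is a few lines of SAP text and one refit per branch, with no new data. The downside is a less conservative test. In the constant branch, size is 5.0% instead of 1.9% only if there is no pre-policy trend, and a continuing trend is flagged more often, as tabulated above. In the linear branch, given entry, the 1-df and joint tests reject a continuing trend in about 21% against 11% at 0.5 SE per year, 3.0% against 1.7% at 1.5, and 5.0% against 2.6% at 3. At 0 to 0.3 SE per year the linear-branch rates are higher for both tests (78% against 68% falling to 42% against 26%), but that branch is then entered in only about 2.5 to 5.5% of cases.
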